2. METHODOLOGY

2.1. Design: Randomized controlled trial of parallel groups.

2.2. Participants:

Sample size and statistical power:

The calculation of the sample size has been made from Objective 1, which focuses on detecting a clinically significant difference in BMI that is the primary outcome measure. Based on previous work that explored weight change in follow-ups after the application of neurocognitive training in people with overweight and obesity (Bazzaz et al., 2017, Kakuschke et al., 2018, Sze et al., 2015), we have selected the smaller sample size (Cohen's $d = 0.46$). With this data, considering the statistical method (models of repeated measures inter and intra subjects), the number of groups ($g = 3$), and assuming an alpha level of 0.05 and a power of 0.80, the resulting sample size calculated with G-Power was 105 participants. To date, no study has conducted a program based on the combination of different neurocognitive tasks that have been proposed as effective for the treatment of obesity, with a 6-month follow-up period. Thus, we opted for a conservative estimate increasing the number of participants to 150. Then, the study could suffer a sample loss of 30% from the initial session to the follow-up at 6 months and the statistical power would be still guaranteed. Previous studies that explored neurocognitive training to lose weight with different follow-up periods have showed smaller attrition rates [i.e., 16% in a 3-month follow up (Carbine et al., 2021); 12.3% in a 2-month follow-up (Forman et al., 2019); 3.4% in a 6-month follow-up (Lawrence et al., 2015)].

Participants:

The participants ($N=150$) will be randomly allocated to three groups: experimental group (neurocognitive intervention; $n=50$), active control group (sham intervention; $n=50$), and control group (treatment as usual; $n=50$).

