2.4. Outcome measures:

Note: The measures have been selected attending to ADOPT (Accumulating Data to Optimally Predict Obesity Treatment), to generate evidence about the efficacy for obesity interventions (MacLean et al., 2018). These measures are marked with an asterisk (*).

(1) Main outcome measure

- a. BMI*: Height and weight will be measured to determine BMI. The weight and height for the calculation of the BMI (kg/m²) will be obtained with a pharmacy digital scale

BMI will check for the results of the whole program (the 4 intervention sessions), and will be registered weekly from session 1 to post-treatment assessment, and will be also registered at follow-ups (3- and 6-months post-treatment). In addition, the week before the pre-treatment assessment session, it will be recorded daily to obtain the baseline weight and then averaged.

(2) Secondary outcomes (changes in cognitive measures, changes in eating and physical exercise behaviors and body measures).

(2.1) Changes in cognitive measures.

- a. Approach-avoidance bias: The approach-avoidance bias will be calculated before and after the 1-week training with the Tilt Task app. Participants should zoom in or out the appetizing and healthy food images that appear on the screen, depending on the presentation format of the image (horizontal or vertical). Approach and avoidance trials will be 50% for each type of image (healthy vs. unhealthy). The average reaction time of the approach (pull) and avoidance (push) trials will be subtracted separately for healthy and unhealthy foods, with the positive and

negative scores representing approximation and avoidance bias, respectively (see Kakuschke et al., 2018 for a full description).

- b. Food inhibition assessment: Using the Food Trainer task, reaction time for the high-calorie and low-calorie foods paired 50% with the go and 50% with the no-go signal will be measured before and after the 1-week training with the app. The average response time for go and no-go items will be calculated according to the type of images (appetizing and healthy foods), and commission errors will be recorded (see Lawrence et al., 2015).

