2. Pre-treatment assessment (session 2; week 1): All participants will complete the following instruments to assess the main and secondary outcomes, and the potential mediators/moderators, exploratory and economic measures: economic and sociodemographic questionnaire; MEDAS; visual analogue scales to evaluate liking, wanting and hunger; food choice task; food liking task; BRIEF-A; IPAQ; DEBQ; FCQ-Tr; PEMS (Coping subscale); RED; DIS; EIEF; WLSE; SOCRATES-00; PSS; mini IPIP; PANAS; UPPS-P; PSRSQ ; FCCS; SF-36, interview about used health resources. The administration order of the tasks will be counterbalanced.
3. Pre-treatment interventions (sessions 3, 4 and 5, week 2):
 - 3.1. Motivational interviewing session: This 90-minute session will be developed in a group format of 5-6 participants.
 - 3.2. Nutrition session: Participants will receive an individualized diet for the following 6 weeks. Videos and brochures about nutrition will be provided, and participants will assist a 60-minute group session with the nutritionist to match and complete relevant information on nutrition and excess weight.
 - 3.3. Physical activity session: Participants will receive physical activity recommendations for the following 6 weeks. Videos and brochures about physical exercise will be provided, and participants will assist a 60-minute group session with the physical exercise instructor to match and complete relevant information on exercise and excess weight.
4. Intervention sessions (sessions 6, 7, 9 and 10; weeks 3, 4, 6 and 7): All sessions will start with Visual Analogue Scales to evaluate hunger, nutrition and physical activity. Each intervention session will be preceded by its pre-treatment evaluation, and followed by its post-treatment evaluation after a week of daily training. The pre and post-treatment evaluation of the impulsive training will be measured by the approach-avoidance bias (with the Tilt-Task app), food choice, the inhibitory control (with the Food Trainer app) and food liking. The pre and post-treatment evaluation of the reflexive training will be

measured by the Now or Later questionnaire for the episodic future thinking training, and the self-registration of nutrition and physical exercise for the implementation of intentions.

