5. Intermediate assessment (session 8; week 5): This assessment will allow the comparison between the interventions for the impulsive and reflexive trainings. It will include: pedometer data; Visual Analogue Scales for liking, wanting and hunger; adherence to diet and physical exercise measured with Visual Analog Scales; Healthy eating with VAS; Exercise habits with VAS; registration of BMI; measure of waist and hip circumference, waist-to-hip ratio and waist-to-height ratio; food choice task; food liking task; PEMS (Coping subscale); DIS; EIEF; WLSE; PANAS; CFCS. The administration order of the tasks will be counterbalanced. After the session, participants will fulfill a self-reported diary with 24-hours food intake.

6. Post-treatment assessment (session 11, week 8): To evaluate the effectiveness of the whole intervention program, the measures of the pre-treatment assessment will be repeated, including: pedometer data; MEDAS, Visual Analogue Scales to evaluate liking, wanting and hunger; adherence to diet and physical exercise measured with Visual Analog Scales; Healthy eating with VAS; Exercise habits with VAS; BMI; measure of waist and hip circumference, waist-to-hip ratio and waist-to-height ratio; food choice task; food liking task; IPAQ; FCQ-Tr; PEMS (Coping subscale); RED; DIS; EIEF; WLSE; PANAS; UPPS-P; CFCS; interview about used health resources. The administration order of the tasks will be counterbalanced. After the session participants will fulfill the self-reported diary with 72-hours food intake.

7. Post-treatment interventions (session 12, week 8): After the post-treatment assessment, participants will have the opportunity to have a second 60-minute group meeting with the nutritionist and another with the physical activity professional, and they will be provided with new 20-minute videos about how to maintain a healthy long-lasting eating and exercise.

After all interventions, participants will be asked to complete a debriefing to register their thoughts and subjective experience about the program.

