8. Follow-up (sessions 13 and 14; week 20 and week 32): Follow-ups at 3 and 6 months after the intervention will include the instruments to obtain the main and secondary outcome measures: pedometer data; Visual Analogue Scales to evaluate liking, wanting and hunger; adherence to diet and physical exercise measured with Visual Analog Scales; Healthy eating with VAS; Exercise habits with VAS; BMI; measure of waist and hip circumference, waist-to-hip ratio and waist-to-height ratio; IPAQ; FCQ-Tr; PEMS (Coping subscale); RED; PSS; mini IPIP; SF-36; interview about used health resources; 72 hours food intake. The administration order of the tasks will be counterbalanced.

Besides, every month after the end of the treatment, participants will be contacted by email and mobile message to explore possible difficulties in following healthy nutritional and exercise habits, and to ask them about their physical activity and healthy goals achievement. The purpose of this contact is, fundamentally, therapeutic adherence.

Participants will be instructed to eat two hours before all evaluation (pre, intermediate and post-treatment, and the two follow-ups) and neurocognitive sessions. Pre, intermediate and post-treatment assessments will be carried out at the same hour.

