4. DATA ANALYSIS PLAN

Once the preliminary analyses for the detection of possible errors in the recording of the data have been made, exploratory and descriptive analyses will be carried out to study the distribution of the variables and the presence of atypical values. The applied inferential statistics will be in accordance with the characteristics of the data obtained (distribution

of the data, qualitative/quantitative nature of the data, etc.) and with the hypotheses proposed in the study. Models of repeated measures two-way ANOVA will be performed, using as dependent variables (DV):

- For objective 1, the change in the BMI between the four moments of assessment [pre (session 1), post-treatment (session 7), 3-month follow-up and 6-month follow-up];
- For objective 2: quantity, type and calories of the food intake; quantity of physical activity; degree of adherence to the diet and physical exercise recommendations; waist circumference and waist to hip ratio; food decision-making and valuation.
- For objective 3: approach-avoidance bias, inhibitory control, food choice task and food liking task will be used to assess the impulsive system; delay discounting and frequency and quantity of food and physical exercise behaviors will be used to assess the executive system. Furthermore, differences on BMI, food behaviors and physical exercise between the groups will be performed to compare the impulsive training and the reflexive training.

Effect sizes for between-group pairwise comparisons will be calculated using the following equation by Morris (2008) to estimate the magnitude of the difference between two groups at two different points in time:

$$d = c_p \left(\frac{(M_{TIME 2, GROUP 2} - M_{TIME 1, GROUP 2}) - (M_{TIME 2, GROUP 1} - M_{TIME 1, GROUP 1})}{SD_{TIME 1}} \right)$$

where M is the mean for each situation, and $SD_{TIME 1}$ refers to the pooled standard deviation of the first measurement moment:

$$SD_{TIME 1} = \sqrt{\frac{(n_{GROUP 2} - 1)SD_{TIME 1, GROUP 2}^2 + (n_{GROUP 1} - 1)SD_{TIME 1, GROUP 1}^2}{n_{GROUP 2} + n_{GROUP 1} - 2}}$$

and c_p is a correction for bias, calculated by:

$$c_p = 1 - \frac{3}{4(n_{GROUP 2} + n_{GROUP 1} - 2) - 1}$$

where n is the sample size for the corresponding group.

Within-group effect sizes will be calculated using Cohen's d (Cohen, 1992):

$$d = \frac{M_{TIME 2} - M_{TIME 1}}{SD_{pooled}}$$

where SD_{pooled} is:

$$SD_{pooled} = \sqrt{\frac{SD_{TIME 1}^2 + SD_{TIME 2}^2}{2}}$$

[figure not shown]

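### The repeated-measures ANOVA for BMI at four moments has no sphericity correction, covariance structure or contrast error term, so its group-by-time test, and possibly its 6-month contrast, can exceed 5% false positives

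*Combined protocol and SAP*

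**What the plan says.** Section 4 (Data analysis plan) states: "Models of repeated measures two-way ANOVA will be performed". For objective 1 the dependent variable is "the change in the BMI between the four moments of assessment". Section 2.2 sizes the trial on the same family of model, "considering the statistical method (models of repeated measures inter and intra subjects").

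Section 3 (Procedure) dates the moments: "Pre-treatment assessment (session 2; week 1"), "Post-treatment assessment (session 11, week 8") and "Follow-up (sessions 13 and 14; week 20 and week 32"). The gaps are therefore 7, 12 and 12 weeks. Section 2.4 says of the pre-treatment value that "it will be recorded daily to obtain the baseline weight and then averaged"; no averaging is described for later moments.

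Two other sentences in section 4 come near the point. One says the inferential statistics will suit the characteristics of the data, with distribution and data type as examples in an open list. The other says corrections for multiple comparisons will be considered. Neither mentions sphericity, an epsilon correction, a covariance structure or the error term for comparing arms at one moment.

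**The concern.** With four moments, the univariate within-subject F test needs sphericity: Var(BMI change) must be equal for all six pairs of moments. Equal variance for a 7-week and a 31-week change would be a special case. The individual diet and exercise plans cover 6 weeks, after which participants are meant to manage on their own, so courses can diverge between weeks 8 and 32.

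If sphericity fails, two different tests are affected:

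- **The omnibus group-by-time F** becomes too liberal.
- **Between-arm contrasts at one moment**, if they use the pooled ANOVA error, get a standard error based on the average of all six change variances, not on the variance of the change being tested.

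Objective 1 asks about short, medium and long term separately, so contrasts by moment are needed. What is at stake is the error rate of the primary outcome, and of the 6-month claim in particular.

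**Working it through.** **The plan's own figure.** Section 2.2 gives d = 0.46, 3 groups, alpha 0.05, power 0.80 and N = 105. Take f = d/2 = 0.23 and the between-factors option, with noncentrality λ = N·m·f² / (1 + (m − 1)ρ). Then m = 4 and ρ = 0.4 give N = 105, while m = 4 and ρ = 0.5 give N = 117. So 105 can be obtained, but it cannot be verified, because the option, the number of measurements and the correlation are not stated. The attrition step reproduces: 150 × 0.70 = 105.

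**Inputs.** Moments at weeks 1, 8, 20 and 32 (section 3); 35 completers per arm (105/3). The BMI covariance and the contrast error term are not in the documents and are assumed below.

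**Contrast formula.** With n per arm, the difference between two arms in mean change has true variance 2V/n, where V is the variance of that change. The pooled ANOVA error uses 2V̄/n, where V̄ is the mean of the six pairwise change variances. Put R = V/V̄. The false-positive rate is P(|Z| > t/√R), with t = 1.968 on 3 × (105 − 3) = 306 degrees of freedom.

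**Worked case: variance proportional to elapsed time (random walk).**

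- The six variances are 7, 19, 31, 12, 24 and 12, so V̄ = 105/6 = 17.5.
- 6 months: R = 31/17.5 = 1.77; 1.968/1.331 = 1.478; rate 13.9%. The standard error is √(17.5/31) = 0.75 of its true value.
- 3 months: R = 19/17.5 = 1.09; rate 5.9%.
- Post-treatment: R = 7/17.5 = 0.40; rate 0.2%.

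**Other assumed covariances.** The 6-month column is the pooled-error contrast from the formula. The F columns are simulated under no effect.

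| Assumed covariance | 6-month contrast | F uncorrected | F, Greenhouse-Geisser |
|---|---|---|---|
| Compound symmetry | 5% | 5.4% | 5.4% |
| Random walk | 13.9% | 8.0% | 4.9% |
| Random walk + error, 5% of final walk variance | 12.6% | 7.0% | 4.7% |
| Random walk + error, 25% | 9.7% | 6.2% | 5.1% |
| AR(1), correlation 0.7 over 31 weeks | 12.9% | 7.4% | 5.0% |
| AR(1), correlation 0.8 over 31 weeks | 13.3% | 7.7% | 4.8% |
| Steady individual slopes, little error | 22% | 12% | about 5% |

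The slopes case has variances proportional to the squared gaps: 49, 361, 961, 144, 576 and 144, mean 372.5, so R = 961/372.5 = 2.58. At the other end, a random walk with error equal to the final walk variance gives 6.9% for the contrast.

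**If change stops after week 8.** Take change SD 1 up to week 8, no further change, and reading error SD 0.25. The three changes from pre have variance 1 + 2 × 0.0625 = 1.125; the other three have 0.125. Then V̄ = 0.625 and R = 1.8, so the pooled contrast has about 14% at every moment, including post-treatment.

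**Spacing.** Equally spaced moments under a random walk have variances 1, 2, 3, 1, 2 and 1, mean 1.67, R = 1.8: 14.2%. Compound symmetry gives 5% at any spacing.

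**Averaged baseline.** If the only departure is a pre value averaged over seven readings, the variances are 8/7 for changes from pre and 2 for the rest, so V̄ = 1.571 and R = 0.727: 2.1%, which is conservative.

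**After repair.** With the variance of the pre-to-6-month change as error term, the simulated contrast rate is 4.8% to 5.3% under every covariance tried. Greenhouse-Geisser degrees of freedom repair the F but leave the pooled contrast at 13.8% under the random walk.

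**The case against.** **The documents fix neither the covariance nor the error term.** This stands. No BMI variance or correlation over time is given, and nothing says contrasts use pooled error. The one pairwise specification, the pre-post effect size for two groups at two times, is not a test and does not settle the matter. A contrast tested with its own change variance has no inflation. So a reader might infer that the plan gives 13% false positives at 6 months, but the documents do not support that as a fact.

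**The unequal gaps look like the cause, and are not.** Equal spacing gives slightly more inflation under the same random walk. The driver is correlation that falls with time apart, or diverging individual courses. Nor does the averaged baseline push the rate up.

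**The post-treatment direction is not fixed.** One might infer that the post-treatment claim becomes too hard to make. That follows only if change keeps accumulating; with a plateau after week 8 it becomes too easy.

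**The plan has flexible wording.** The list of data characteristics is open-ended, so an analyst could invoke it. It sets no rule, though, and would leave the choice until the data are seen. Multiplicity corrections do not repair a wrong error term: with Bonferroni over three contrasts (1.67% each), the pooled 6-month contrast under the random walk is still 7.1%.

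**The sample size is not shown to be wrong on this ground.** The option that can reach 105 is a between-factors test, which takes no epsilon.

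**Conclusion.** The point holds as a gap in the named primary analysis. An uncorrected repeated-measures ANOVA of BMI at four moments over 31 weeks relies on an assumption unlikely to be met, and the plan states no safeguard.

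As an illustration, the uncorrected group-by-time F has about 7% to 12% type I error where sphericity clearly fails. It is nearer 6% where reading error is a larger share of the variance, and 5% under compound symmetry. Conditional on pooled-error contrasts, the 6-month comparison has about 5% to 22%, and about 13% to 14% under a random walk or highly correlated AR(1). The post-treatment comparison can err either way.

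These figures rest on assumed covariances, no treatment effect and 35 per arm. Section 4 also labels pre and post as sessions 1 and 7, where section 3 has sessions 2 and 11. This should be reconciled, but matters little here: taking pre at week 0 gives variances 8, 20, 32, 12, 24 and 12, R = 32/18 = 1.78, and moves the random-walk figure only from 13.9% to 14.0%.

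The change should be made before analysis; it does not call the design into question.

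**What to change.** In section 4, for BMI and other outcomes with more than two moments, do one of the following:

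- **Preferred:** fit a repeated-measures mixed model with group, moment and their interaction and an unstructured covariance across moments. Take the between-arm contrasts at post-treatment, 3 months and 6 months from it.
- **If the ANOVA is kept:** report the Greenhouse-Geisser corrected group-by-time F, and test each between-arm contrast with the variance of that moment's own change from pre, not the pooled error. Both parts are needed, since the epsilon correction does not repair pooled-error contrasts.

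Section 2.2 needs no epsilon on this account unless the G-Power option used took one; if it did, state the value.

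The cost is one or two sentences and no new data. The omnibus test loses some degrees of freedom, and the 6-month interval may be wider. Writing it down now also prevents the error term from being chosen after results are seen.

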1. STARTING HYPOTHESES AND GENERAL OBJECTIVE

HYPOTHESIS: The treatment of excess weight with a comprehensive program based on experimental knowledge about the functioning and modification of the impulsive and executive systems will be effective for the treatment of overweight and obesity. Thus, the neurocognitive training will reduce body mass index (BMI) in people with overweight and obesity, compared to a sham treatment and to only usual treatment. In addition, the neurocognitive program will improve other anthropometric measures (waist circumference, waist-to-hip and waist-to-height ratios), lifestyle behaviors (eating behavior and physical activity), as well as cognitive processes (approach-avoidance bias, food inhibition, food liking and delay of gratification). Finally, the program will show its efficiency in the economic balance of cost-effectiveness and cost-utility.

GENERAL OBJECTIVE: To determine the effectiveness of a comprehensive neurocognitive program for the treatment of excess weight.

1.1. Specific Aims:

Objective 1: To examine the effectiveness of a comprehensive neurocognitive training to reduce BMI in the short, medium and long term (post-treatment, 3-month follow-up and 6-month follow-up).

Objective 2: To study the effectiveness of the comprehensive neurocognitive program to change food behaviors, physical activity and body measures.

Objective 3: To investigate which active ingredients have an impact on the results of the program as outlined below:

3.1. To study the effectiveness of the impulsive training (approach-avoidance bias modification and improvement of inhibitory control) to reduce the approach bias to appetitive foods, increase the inhibitory control, improve the food decision making and modify the valuation of healthy and unhealthy foods.

3.2. To study the effectiveness of reflexive training (implementation of intentions and episodic future thinking) to improve behaviors related to implementation of intentions in healthy eating and physical activity, and to increase delay of gratification.

3.3. To compare the effectiveness of the neurocognitive training (impulsive and reflexive) to reduce BMI and body measures, and to improve food behaviors and physical activity.

3.4. To study the variables related to cognition, affect, stress and non-homeostatic food intake, motivation and personality to predict or mediate the intervention results.

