c. Implementation of Intentions technique. Following the process described by Benyamin et al. (2013), each participant establishes one intention related to food and one related to exercise, and writes when, where and how they will implement each one, possible inconveniences to do it, and how they will overcome them. Furthermore, according to Adriaansen et al. (2009), motivational cues (why I eat) will be considered (negative emotions –I'm bored; social motives –eat a piece of cake you are offered in a party; politeness/conformity with others' expectations; pleasure). The implementation of intentions related to food will be written in format: "if... then..." [e.g., "If I come home from work hungry in the evening, then I will eat an apple" (Adriaansen et al., 2009)]. This format allows for the consideration of the health goals and medium and long-term objectives for each of the participants. The intention related to food will focus on unhealthy snacking habits whenever possible. For participants without snacking behaviors personalized food goals will be used. The sham condition participants will choose 10 items of healthy foods to eat in the moment that they want to eat unhealthy food and they will order a list of physical activities that they would like to do.

d. Episodic Future Thinking. Participants will decide health-related goals and anticipate future personal events at various time points (e.g., next month, 2-3 months and 4-6 months), from which contextual, temporal and emotional cues should be obtained. Goals and future events will be matched to generate episodic future thinking that includes the necessary keys to facilitate their effectiveness (O'Neill et al., 2016). For the sham training, habits and positive recent past events (1 day ago, 2 days ago, 1 week ago) unrelated to food or exercise will be considered. Participants will write their three cues on paper and/or their cell phones, and they will read and visualize them daily at home.

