Based on Cohen's (1992) rule of thumb, clinical significance of change will be reflected by medium within-group effect sizes ($d \geq .5$).

Mediation and/or moderation analysis will be carried out to study the role of variables related to cognition, affect, stress and non-homeostatic food intake, motivation and personality on the program outcome measures.

In addition, possible differences in the program outcomes will be assessed based on sex and weight classification (overweight and obesity -type I and type II).

All the analyses described will be carried out following an intention to treat strategy (ITT) and analysis per protocol (PP). Corrections will always be considered to control for multiple comparisons.

- For objective 4, the average cost and effectiveness (BMI and QALY) for the 3 groups (intervention, sham and treatment as usual) will be estimated. The ratios of incremental cost effectiveness and incremental utility cost will be calculated as the cost and effectiveness difference (BMI and QALY) for the 3 groups. All the analyses will be carried out according to the methodological recommendations for Spain (López-Bastida et al., 2010). The perspective of the health system will be used, including only direct costs. The uncertainty of the results will be carried out through various deterministic sensitivity analysis (AS) and a probabilistic one using nonparametric bootstrapping methods of 1000 iterations (Luce et al., 2001) that will allow to represent the cost-effectiveness plane and the Acceptability curve. The AIP will estimate the variation that the introduction of neurocognitive training would imply for the budget of the public health system, based on the estimated costs of the alternatives compared and the estimated number of patients expected to benefit from the program. Likewise, univariate and multivariate AS will be performed to analyze different budgetary scenarios based on a possible variation in the cost variables and number of beneficiary patients.

**Only in experimental and active control groups (what is not in italics is done by all three groups: experimental, active control, and control) //* Assessment task

Figure 1: Procedure of the program.

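### Does the 30% loss allowance fail for the two BMI comparisons (versus sham and versus usual treatment)?

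*Combined protocol and SAP*

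**What the plan says.** Section 2.2 (sample size and statistical power) bases the calculation on Objective 1, with BMI as the primary outcome. It takes d = 0.46, a repeated-measures model with between- and within-subject parts, and three groups: "assuming an alpha level of 0.05 and a power of 0.80, the resulting sample size calculated with G-Power was 105 participants". The number is then raised to 150, and the trial is said to tolerate a "sample loss of 30% from the initial session to the follow-up at 6 months and the statistical power would be still guaranteed". Three published attrition rates are given as reassurance: "16% in a 3-month follow up", 12.3% at two months and "3.4% in a 6-month follow-up".

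The hypothesis in section 1 is that training lowers BMI "compared to a sham treatment and to only usual treatment". Section 4 analyses BMI at four time points by repeated-measures ANOVA and defines a pairwise effect size "to estimate the magnitude of the difference between two groups at two different points in time". It adds: "Corrections will always be considered to control for multiple comparisons". No method of correction is named, and no power is stated for either pairwise comparison.

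**The concern.** A G*Power ANOVA calculation with three groups sizes an overall F test. Rejecting that test confirms neither half of the hypothesis, which needs training to differ from sham and from usual treatment. A two-arm comparison uses two thirds of the participants and may be tested at a stricter level, so 80% for the overall test can mean less for each pair.

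If so, a non-significant result against sham after a loss of, say, 25% would be read as coming from a trial with 80% power when the real figure was lower. The sham comparison is the one that isolates the training, and the sham has some plausible content of its own: "The sham condition participants will choose 10 items of healthy foods to eat in the moment that they want to eat unhealthy food". If it is partly active, power against it falls further.

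**Working it through.** **1. The plan's own figure.** 150 x (1 - 0.30) = 105, so the loss allowance is exact for the test behind the 105.

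**2. Can the 105 be reproduced?** Section 2.2 does not give the number of measurements, the correlation or the G*Power test option with the calculation. Taking f = d/2 = 0.23 (an assumption; the plan states no conversion) and four visits:
- Between-subject test, lambda = N f² m / (1 + (m-1) rho): 117 at rho = 0.5; 105 at rho of about 0.40.
- Group-by-time interaction, lambda = N f² m / (1 - rho), sphericity assumed: 36 at rho = 0.5; 69 at rho = 0.

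So 105 can be obtained, but not uniquely. The interaction, which is the term matching section 4's change in BMI over four moments, needs far fewer.

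**3. The unfavourable reading: take 105 = 80% as given.** Put the training mean at 0, sham at a and usual treatment at b (in error SD units), with n per arm:
- three-group lambda = n(2a² + 2b² - 2ab)/3
- weaker pair lambda = n min(a,b)²/2

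The ratio is largest when a = b: (n a²/2) / (2n a²/3) = 0.75.

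| | 2-df group test | four-visit interaction |
|---|---|---|
| lambda for 80% at N = 105 | 9.92 (df 2, 102) | 13.91 (df 6, 306) |
| 0.75 lambda | 7.44 | 10.43 |
| weaker pair, unadjusted | 77.1% (df 1, 102) | 77.5% (df 3, 306) |
| weaker pair, Holm over two (simulated) | 72.9% | 73.5% |
| weaker pair, Bonferroni | 67.5% | 68.2% |

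On this reading 80% is kept up to a loss of 25-26% unadjusted, 18-20% with Holm and 9-12% with Bonferroni.

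**4. The plan's effect size instead of a back-solved lambda.** For the interaction with f = 0.23, four visits and rho = 0, lambda at 105 is 105 x 0.0529 x 4 = 22.2. The weaker pair with equal controls has 0.75 x 22.2 = 16.7 on 3 and 306 df: 94% unadjusted, 90% Bonferroni. At rho = 0.5 both exceed 99%. A change between two visits under a constant post-treatment effect (two thirds of 16.7, or 11.1, on 1 df) has 91% unadjusted and 86% Bonferroni at rho = 0. There is no shortfall. One appears only with strong non-sphericity and near-zero correlation together (epsilon 0.5, rho 0: 77% and 67%).

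**5. Sensitivity to the form of the pairwise test.** Return to step 3's four-visit reading (105 = 80%). One contrast matched to the whole effect pattern has 90% unadjusted, 88% with Holm and 84% with Bonferroni, so the 30% allowance would hold. The two-visit change has 74%, 70% and 64%. The conclusion therefore turns on a test form that the plan does not fix.

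**6. At the cited attrition.** Still taking 105 = 80% and equal controls (2-df / four-visit):

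| Loss | Completers | Unadjusted | Holm | Bonferroni |
|---|---|---|---|---|
| 16% | 126 | 84 / 85% | 81 / 83% | 76 / 78% |
| 12.3% | 132 | 86 / 87% | 83 / 85% | 78 / 80% |
| 3.4% | 145 | 89 / 90% | 87 / 89% | 83 / 84% |

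**The case for a change.** The best argument for a change is that step 3 needs no guess about effect size, correlation or visits. It takes the sponsor's figure at face value, and even with no correction the allowance for the weaker comparison is 25-26%, below 30%. Section 4 contemplates a correction, so the unadjusted case is the lenient one. At 16% loss, Holm keeps 80% and Bonferroni does not, so the unnamed method matters at a rate the plan itself cites. If the sham lies a quarter or half of the way from usual treatment to training (an assumed range), Holm power against it at 105 is 58-59% or 30-34%. A few sentences would settle the matter without touching the sample size.

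Part of this stands. The 80% should not be read as covering each pairwise comparison, and the calculation inputs, the pairwise contrast and the correction are not written down.

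The rest is weaker. Step 3 relies on 105 being exactly 80%, which cannot be verified, and it sets aside the one effect size the plan gives. Holm, and a repeated-measures term restricted to two arms, are choices brought to the plan. Prescribing that term would fix a 3-df test with 73.5% power on the four-visit reading, where a matched contrast has 88%. Writing an 18% allowance into section 2.2 would enter a number that the missing inputs could overturn. The 16% rate is a three-month figure; the only cited six-month rate is 3.4%, where Bonferroni still gives 83-84%. The calculation also treats a lost participant as contributing nothing, whereas BMI is recorded weekly to post-treatment and again at three months under an intention-to-treat strategy (although no missing-data method is named). Nothing in the documents sizes the sham's effect.

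**Conclusion.** No stated figure is wrong. The 30% allowance is arithmetically consistent with the three-group model it is attached to, and section 2.2 makes no power claim for the pairwise comparisons. Whether those comparisons fall short at 105 is undetermined. Power for the weaker one is at most 77% unadjusted, or 73-74% with Holm, if 105 is exactly 80%, the controls are equal and the same term is restricted to two arms. It is 94% unadjusted, or 90% with Bonferroni, for the planned group-by-time term at f = 0.23, zero correlation and sphericity.

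At every cited attrition rate Holm keeps at least 81% with equal controls, even on the unfavourable reading, and the 30% is presented as a margin above those rates. What is left is missing detail: the G*Power options, the contrast for each BMI comparison and the correction. Analysts who are blind to group, as section 2.2 provides, can settle the last two sensibly before the results are known. The trial would enrol 150 on any of these readings. No change to the plan follows.
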